16.4.4 Secondary Vaccine Response Endpoints

The following secondary vaccine response endpoints are to be analyzed, in any order:

- Proportion of subjects with a positive serum IgG response to tetanus toxoid at Week 16 (\geq 2-fold increase in anti-tetanus IgG concentration from baseline in subjects with pre-vaccination anti-tetanus IgG concentration \geq 0.1 IU/mL OR \geq 0.2 IU/mL anti-tetanus IgG concentrations in subjects with pre-vaccination anti-tetanus IgG concentrations $<$ 0.1 IU/mL)
- Proportion of subjects with serum anti-tetanus IgG concentrations of \geq 0.1 IU/mL at Week 16
- Proportion of subjects with serum anti-tetanus IgG concentrations of \geq 1.0 IU/mL at Week 16
- Proportion of subjects with a positive serum bactericidal antibody response to meningococcal serogroup C polysaccharide at Week 16 (4 weeks post-vaccination) defined as \geq 4-fold increase in SBA reciprocal titer from baseline

- Proportion of subjects with a positive serum bactericidal antibody response to meningococcal serogroup C polysaccharide at Week 16 defined as SBA reciprocal titer ≥ 8

All secondary vaccine response endpoints will be analyzed on the mITT population.

For all secondary vaccine response endpoints, the same analysis methods as for the primary vaccine response endpoint will be utilized.

Subgroup analyses may be conducted based on selected demographic variables of interest, and by vaccine response for the endpoints described in Section 16.4, if needed.

Further details on all vaccine response endpoints and analyses will be included in the SAP.

[figure not shown]
CCI

This document is confidential.

Page 102 of 133

CCI

Discrete binary secondary efficacy endpoints will be analyzed in the same manner as the primary vaccine response endpoint, using a CMH method to estimate the risk difference and two-sided 95% CI, stratified by baseline CCI. Given that the population for efficacy is the ITT population, the analysis will be conducted with any missing data at the time point imputed as Non-Responder.

Continuous secondary endpoints will be analyzed primarily as observed (ie, non-imputed) using a mixed-effect model for repeated measures approach, including baseline CCI as factor and baseline result for the endpoint as covariate. The estimated treatment difference for each endpoint at each visit will be displayed in the summary of statistical analysis together with the two-sided 95% confidence interval and associated p-value. An unstructured covariance matrix will be used to model the correlation among repeated measurements, and the Kenward-Roger adjustment will be used with restricted maximum likelihood for statistical inference.

Additionally, an analysis of covariance approach, including baseline CCI as factor and baseline result as covariate will be conducted for the specific secondary endpoint, based on data as observed.

Further to the above efficacy analyses, for all secondary efficacy endpoints, any missing data at any post-baseline visit (including Week 16) will be imputed utilizing multiple imputation (MI) using missing not at random (MNAR) with a controlled-based pattern mixture approach.

This document is confidential.

Page 103 of 133

The MI will be carried out as follows:

- 1) Fifty (50) imputed datasets with a monotone missing pattern will be multiply created using SAS MI procedure based on the observed data (Markov-Chain-Monte-Carlo method). The seed to be used is 118380 (the protocol number).
- 2) Each of the imputed datasets will be used to generate 50 complete datasets, using a regression method and the profiles from placebo subjects to impute the missing data of subsequent visits, including factors for treatment and randomization strata, and any applicable baseline as covariate.
- 3) The complete datasets will be modelled for the endpoint as specified above for discrete binary or continuous endpoints
- 4) The results from the analysis of the multiple imputed datasets will be combined by the MIANALYZE procedure of the SAS system.

Further details will be provided in the SAP.

For subjects in receipt of rescue medication at any point during the study, their data collected post-rescue intake will be set to missing, and analyzed in the manner above as observed and/or imputed. An additional analysis including all collected data as observed will also be conducted, with no adjustment for data collected post-rescue medication intake.

A summary of the approach for analysis of the secondary efficacy endpoints on the ITT population is as follows:

Endpoint Type	Analysis	Imputation Method	Adjustment for Data Post-Rescue Med Intake
Binary	CMH	Non-Responder	Set to missing and impute
		MI	Set to missing and impute
		OC	Set to missing (with no imputation) Analyzed as seen (OC)
			Set to missing (with no imputation) Analyzed as seen (OC)
Continuous	MMRM	OC	Set to missing (with no imputation) Analyzed as seen (OC)
		ANCOVA	MI

Abbreviation(s): ANCOVA= analysis of covariance; CMH= Cochran-Mantel-Haenszel; MI= multiple imputation; MMRM= mixed-effect model for repeated measures; OC=observed case.

Further details will be included in the SAP.

16.6 Safety Analysis

All safety analyses will be conducted on the SAF, by treatment group.

All reported AEs will be coded using the Medical Dictionary for Regulatory Activities (MedDRA), version 22.0 or later. The treatment-emergent period will be defined as the period of time from the first dose date of study treatment through 12 weeks (84 days) after the last dose of study treatment (ie, up to the follow-up visit for completers), or the date of rollover to the LTE study (SPR.118163), whichever is earlier. The incidence of TEAEs (events with onset dates on or after the start of the study drug), drug-related TEAEs, SAEs, TEAEs leading to study drug discontinuation and treatment-emergent AESIs will be included in incidence tables, summarized by System Organ Class (SOC) and Preferred Term (PT). Events with missing onset dates (and no data to suggest the

[figure not shown]
This document is confidential.

event stopped prior to study treatment start) will be included as treatment-emergent. The incidence of TEAEs by severity, counting multiple AEs under SOC and PT for a subject at the maximum severity will be presented. All AEs will be listed by subject, along with information regarding onset, duration, relationship and severity to study drug, action taken with study drug, treatment of event, and outcome.

Clinical laboratory data and vital signs will be summarized using descriptive statistics, including observed values and change from baseline values, as well as numbers of subjects with values outside limits of the normal range, including shifts from baseline at each time point.

Summary tables will be provided for 12-Lead ECG, Physical Examination (Full and Symptom-oriented), ACT, PEF, and Respiratory Exam, by treatment group and visit where appropriate. Listings will also be provided.

[figure not shown]
CCI

This document is confidential.

Page 106 of 133

CCI

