	
The study consists of a 2- to 4-week screening period, a 16-week treatment period, and an 8-week follow-up period (12 weeks after the last study drug injection).
 
The screening period will evaluate subject eligibility. Subjects will apply a moisturizer at least once daily, beginning at screening. Subjects using a stable regimen of low- or medium-potency topical corticosteroid (TCS) with or without topical calcineurin inhibitor (TCI) at the screening visit (ie, ≥ 14 days prior to the baseline visit) should continue their therapy regimen. Subjects not using a stable regimen of TCS with or without TCI at the screening visit should not use these topical therapies during the study unless required as rescue therapy.
 
At the baseline visit, subjects will receive a loading dose of nemolizumab (60 mg) or placebo via 2 subcutaneous injections. Nemolizumab (30 mg) or placebo will then be administered via a single subcutaneous injection every 4 weeks (Q4W) at Week 4, 8, and 12. At the Week 12 visit, subjects will also receive single doses of tetanus toxoid, reduced diphtheria toxoid, and acellular pertussis PPD and quadrivalent meningococcal conjugate PPD vaccines. Clinical assessments will occur according to the schedule of assessments. Refer to Figure 1 for an overview of the study design.
 
Subjects will continue to apply a moisturizer at least once daily throughout the study. Subjects using background topical therapy (TCS with or without TCI) from the screening visit will continue use in the treatment period, which should be adjusted according to the disease activity and tolerability, based on investigator clinical judgment. (Subjects not using background topical therapy from the screening visit should not apply background topical therapy in the study.) If deemed to be medically necessary by the investigator (eg, to control intolerable AD signs/symptoms), topical and/or phototherapy rescue therapies can be prescribed to any subject at any time during the study, except during the screening period.
 
Subjects who complete the Week 16 treatment period may be eligible to enroll into a long-term extension (LTE) study (Protocol 118163). The follow-up visit is not required for subjects who participate in the LTE study.
 
Subjects who decline or are not eligible to enter into the LTE study will complete a follow-up visit at Week 24 (12 weeks after their last study drug injection).
 
Subjects who discontinue the study prematurely should complete an early termination visit and a follow-up visit 12 weeks after their last study drug injection.
 
An independent data monitoring committee (IDMC) will review and monitor subject safety throughout the study, and an independent adjudication committee (IAC) will review all asthma-related AEs.

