Subjects will continue to apply a moisturizer at least once daily. Subjects using background topical therapy (TCS with or without TCI) from the screening visit will continue use in the treatment period, which should be adjusted according to the disease activity and tolerability, based on investigator clinical judgment. (Subjects not using background topical therapy from the screening visit should not apply background topical therapy in the study.) If deemed to be medically necessary by the investigator (eg, to control intolerable AD signs/symptoms), topical and/or phototherapy rescue therapies can be prescribed to any subject at any time during the study, except during the screening period.

Subjects who complete the Week 16 treatment period may be eligible to enroll into an LTE study (Protocol 118163).

Follow-Up Period

The follow-up visit is not required for subjects who participate in the LTE study.

Subjects who decline or are not eligible to enter into the LTE study will complete a follow-up visit at Week 24 (12 weeks after their last study drug injection).

[figure not shown]
Subjects who discontinue the study prematurely should complete an early termination visit and a follow-up visit 12 weeks after their last study drug injection.

The follow-up visit will be conducted 8 weeks after completing the treatment period and/or 12 weeks after the last study drug injection. Twelve weeks corresponds to approximately 5 half-lives when nemolizumab 30 mg is dosed subcutaneously every 4 weeks.

An IDMC will review and monitor subject safety throughout the study, and an IAC will review all asthma-related AEs. Details on the IDMC and IAC, including the plan of analysis for outputs, the composition of the committees, the procedures, roles, responsibilities and their communications are provided in the IDMC and IAC charters, respectively.

An overview of the study design is present in [Figure 1](#).

Figure 1: Study Design

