9.7.1 Early Termination Visit

Subjects may discontinue from the study or discontinue the study treatment only and continue to participate in the study.

Subjects who prematurely discontinue from the study should undergo final study assessments according to the following guidelines:

- Subjects discontinued from the study during the treatment period on/before the Week 16 visit should attend an early termination visit.
- A follow-up/final visit is required 12 weeks after the last study drug administration.

Subjects who prematurely discontinue the study drug will be asked to continue participation in the study; however, subjects who discontinue the study drug prior to Week 12 should not be vaccinated. Subjects will be asked to return for all remaining visits and assessments (including daily assessment of pruritus, sleep disturbance, etc). Participation will continue until the subject completes the final study visit or otherwise discontinues study participation.

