## 10.3. Adverse Events / Adverse Drug Reactions

Adverse events (AEs) will be coded using MedDRA Version 25.0.

Treatment-emergent AEs (TEAEs) is defined as AEs with an onset date on or after the first dose date of study treatment. Partially missing date will be handled using the algorithm described in Section 6.3. AE

related to study drug is defined as AE with a relationship to study drug reported as 'Reasonable Possibility' or missing.

Summary table for adverse events will include the number and percent of subjects and the numbers of events by treatment group and by System Organ Class (SOC) and Preferred Term (PT). SOC and PT within each SOC will be sorted by descending overall frequency. Subjects who have multiple events in the same SOC and the same PT within each SOC will be counted only once in the subject counts, but all events will be considered and presented (if applicable). For summary by maximum severity, subjects who experience multiple occurrences of an AE, the most severe category for each SOC and for each PT within each SOC will be considered in the summary.

The summary tables for following TEAEs will be presented:

- Overall Summary: summary of the number and percentage of subjects reporting TEAEs, TEAEs by
  maximum severity, serious TEAEs, study drug-related TEAEs, drug-related serious TEAE, study
  drug-related TEAEs by maximum severity, treatment-emergent AESI, Confirmed or suspected
  COVID-19 infection, TEAEs leading to study drug withdrawal, TEAEs leading to study drug
  interruption, TEAEs leading to study discontinuation, and TEAEs leading to death
- The total number and incidence of TEAEs by SOC and PT
- The total number and incidence of Serious TEAEs by SOC and PT
- The total number and incidence of TEAEs related to study drug by SOC and PT
- The total number and incidence of serious TEAEs related to study drug by SOC and PT
- The total number and incidence of TEAEs by SOC, PT, and maximum severity
- The total number and incidence of drug-related TEAEs by SOC, PT, and maximum severity
- The total number and incidence of TEAEs leading to temporary interruption of study drug by SOC and PT
- The total number and incidence of TEAEs leading to permanent discontinuation of study drug by SOC and PT
- The total number and incidence of TEAEs leading to study discontinuation by SOC and PT
- The total number and incidence of TEAEs of special interest by SOC and PT

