#### 15.2.5.2. Table Conventions

- Units will be included where available.
- If the categories of a parameter are ordered, then all categories between the maximum and minimum category are presented in the table, even if n=0 for all treatment groups in a given category that is between the minimum and maximum level for that parameter.
- If the categories are not ordered (e.g., Medical History, Reasons for Discontinuation from the Study, etc.), then only those categories for which there is at least 1 subject represented in 1 or more groups are included.

- Unless otherwise specified, the estimated mean, median, Q1 and Q3 for a set of values are printed out to 1 more significant digit than the original values, and standard deviations are printed out to 2 more significant digits than the original values. The minimum and maximum should report the same significant digits as the original values.
- P-values are output in the format: "0.xxx", where xxx is the value rounded to 3 decimal places. Every p-value less than 0.001 will be presented as <0.001. If the p-value is returned as >0.999, then present as >0.999.
- Percentage values are printed to one decimal place, in parentheses with no spaces, one space
  after the count (e.g., 7 (12.8%), 13 (5.4%)). Unless otherwise noted, for all percentages, the
  number of subjects in the analysis set for the treatment group will be the denominator. Percentages
  after zero counts should not be displayed and percentages equating to 100% are presented as
  100%, without decimal places.
- Where a category with a subheading (such as system organ class) has to be split over more than one page, output the subheading followed by "(cont)" at the top of each subsequent page. The overall summary statistics for the subheading should only be output on the first relevant page.

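### TEAE follow-up ends at LTE rollover for some subjects and up to eight weeks later for others, but the SAP plans only crude percentages, so unequal rollover by arm could bias the comparison in either direction

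*Protocol*

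**What the plan says.** Protocol 16.6 opens the treatment-emergent period at the first dose and runs it "through 12 weeks (84 days) after the last dose of study treatment (ie, up to the follow-up visit for completers"). A second limit applies to subjects who enter the LTE, whose period stops there if that comes sooner: "or the date of rollover to the LTE study (SPR.118163), whichever is earlier". Rollover comes after Week 16: "Subjects who complete the Week 16 treatment period may be eligible to enroll into an LTE study (Protocol 118163"). For those who roll over, the Synopsis says "The follow-up visit is not required for subjects who participate in the LTE study". For the other completers, Protocol 7.1 says "Subjects who decline or are not eligible to enter into the LTE study will complete a follow-up visit at Week 24". For subjects who leave early, Protocol 9.7.1 says "A follow-up/final visit is required 12 weeks after the last study drug administration".

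SAP 10.3 counts an AE as treatment-emergent if it starts on or after the first dose, and gives no end of window. It continues: "Summary table for adverse events will include the number and percent of subjects and the numbers of events by treatment group". Under SAP 15.2.5.2, unless noted otherwise, the "number of subjects in the analysis set for the treatment group will be the denominator". The safety table index is readable (Tables 14.3.1.1 to 14.3.1.15). It lists no exposure-adjusted rate, no time-to-event summary and no TEAE table restricted to the treatment period.

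SAP 6.2.3 defines treatment and follow-up periods, and SAP 7.6 splits rescue medication by them, but the TEAE tables are not split. The exposure duration in SAP 10.1 stops at the last injection. The visible disposition list in SAP 7.1 does not count LTE rollover by arm.

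**The concern.** A crude percentage over all treated subjects compares arms fairly only if the arms are observed for similar lengths of time. Here the length depends on whether a subject enters the LTE. That is settled after treatment, by choice or eligibility, and treatment may influence it, so randomization does not guarantee that rollover is balanced. If it is not, the arm with more rollover has less time in which to record a TEAE.

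Safety is a stated secondary objective and will be read from these percentages. Unequal rollover could create a small apparent difference or hide part of a real one. The planned outputs would not let a reader tell which, because neither rollover nor observation time is reported by arm. Table 14.1.1.3 accounts for subjects by visit, but absence at Week 24 does not by itself separate rollover from loss to follow-up.

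**Working it through.** **Window lengths.** The last scheduled dose is at Week 12, which is Day 12 × 7 + 1 = 85. Adding the protocol's 84 days gives Day 169, which matches the Week 24 target in SAP 6.4. Week 16 is Day 16 × 7 + 1 = 113, also as in SAP 6.4. A completer who does not roll over therefore has 24/16 = 1.5 times the window of an LTE entrant. For early discontinuers, 12 weeks after the last dose ends at Week 12 if only baseline was dosed, at Week 16 after a last dose at Week 4, and at Week 20 after a last dose at Week 8. Some are observed for less time than an LTE entrant and some for more.

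**Size of a possible shift.** The documents give neither a TEAE rate nor a rollover rate for this trial, so both are assumed. Assume also the same constant hazard in both arms and that every subject completes Week 16. Let c16 and c24 be the incidence by Weeks 16 and 24, and r the share rolling over.

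- λ = −ln(1 − c16)/16
- c24 = 1 − exp(−24λ) = 1 − (1 − c16)^1.5
- Crude incidence in an arm = r·c16 + (1 − r)·c24
- Spurious difference, arm B minus arm A = (rA − rB) × (c24 − c16)
- Standard error of a difference at 123 per arm (Protocol 16.9) ≈ √(2·c16·(1 − c16)/123)

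| c16 | c24 | c24 − c16 (points) | 10-point rollover gap | 20-point rollover gap | Standard error (points) |
|---|---|---|---|---|---|
| 5% | 7.4% | 2.4 | 0.2 | 0.5 | 2.8 |
| 30% | 41.4% | 11.4 | 1.1 | 2.3 | 5.8 |
| 45% | 59.2% | 14.2 | 1.4 | 2.8 | 6.3 |
| 60% | 74.7% | 14.7 | 1.5 | 2.9 | 6.2 |

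With equal rollover the shift is zero. Otherwise the arm with more rollover shows the lower percentage. Even at a 20-point gap the shift is under half a standard error (2.3/5.8 = 0.40; 2.9/6.2 = 0.47).

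**Masking.** Take a placebo risk of 50% by Week 16 and a true hazard ratio of 1.2.

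- Week 16 risk on nemolizumab is 1 − 0.5^1.2 = 56.5%, a difference of 6.5 points.
- Week 24 risks are 1 − 0.5^1.8 = 71.3% on nemolizumab and 1 − 0.5^1.5 = 64.6% on placebo.
- With rollover of 90% on nemolizumab and 70% on placebo, crude incidence is 0.9 × 56.5 + 0.1 × 71.3 = 58.0% against 0.7 × 50 + 0.3 × 64.6 = 54.4%. The difference falls to 3.6 points.
- With 90% against 50%, placebo is 0.5 × 50 + 0.5 × 64.6 = 57.3%, and the difference falls to 0.6 points.

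**What the added tables would show.** Under equal constant hazards, incidence through Week 16 is c16 in both arms and the rate per person-time is λ in both. Both comparisons then give no difference, whatever the rollover.

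**The case against.** A reader might infer that the planned tables will show a false safety difference. The documents do not support that. The bias needs rollover to differ by arm. No rollover figure is given, and nothing indicates that a gap exists or which way it would run. The shifts above are small against sampling error, and smaller still in absolute terms for uncommon events (0.5 points at 5% risk and a 20-point gap). No test, margin or decision rule is attached to TEAEs, and the primary endpoint, read at Week 16, is untouched.

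A constant hazard may also overstate the shift. AEs are elicited by questioning at visits (Protocol 13.1). Protocol 7.1 describes one follow-up visit after Week 16, against dosing visits every four weeks before it, and no study drug or study vaccine is scheduled after Week 12.

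A reader might further infer that Weeks 16 to 24 are simply off-drug and that the main tables should be cut at Week 16. That goes too far. The half-life is about two weeks (Protocol 5.2.2), and the 12-week follow-up was chosen to span about five half-lives (Protocol 7.1 and 7.2). Those weeks are a period of declining exposure that the protocol deliberately counts as treatment-emergent. Cutting the main tables at Week 16 would take those events out of the headline display.

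All of this stands, and it limits the size of the point and the remedy. It does not remove the gap. A systematic shift does not average out as noise does, and the planned outputs give no means of seeing whether one is present. Onset dates are listed, so the tables could be produced later on request, but it is better to specify them in advance.

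**Conclusion.** The point holds as a cheap improvement. TEAE observation time differs by design between LTE entrants, other completers and early discontinuers, and the planned tables ignore this. If rollover differs by arm, the crude comparison could be biased in either direction, by about 1.1 to 1.5 points per 10-point gap and 2.3 to 2.9 points for a 20-point gap, against a standard error of about 6 points. These figures assume a constant hazard, 30% to 60% incidence by Week 16 and no early discontinuation. Rollover by arm is unknown, so neither the presence nor the direction of a bias can be stated.

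One part needs no assumption: SAP 10.3 omits the end of the treatment-emergent window that Protocol 16.6 sets, and the two texts should be reconciled.

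**What to change.** Keep the planned treatment-emergent tables, and make four changes to the SAP:

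1. In 10.3, restate the protocol's end of window: 84 days after the last dose or LTE rollover, whichever is earlier.
2. In 10.3, add exposure-adjusted incidence rates by arm for TEAEs, serious TEAEs and AESIs. Divide subjects with an event by total time from first dose to first event or end of the treatment-emergent window. Do not use the SAP 10.1 duration.
3. In 10.3, add a supplementary TEAE table for onset through Week 16. Show follow-up-period TEAEs separately, with only subjects who entered follow-up as denominator. State the cut for early discontinuers, because under SAP 6.2.3 their treatment period can end before Week 16. This table also covers the case where the hazard is not constant, which a person-time rate alone does not.
4. Report LTE rollover and TEAE observation time by arm, for example with the disposition summary in 7.1.

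The tables use onset, dosing, rollover and visit dates that the planned analysis already needs. Design, dosing and data collection do not change. The downside is a few more safety tables. If the SAP is no longer open to revision, Protocol 16 provides for later analysis changes to be documented in the clinical study report.
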